Study Design and Participants

This study was conducted as a randomized, sham-controlled, single-blind clinical trial to investigate the combined effects of Botulinum Toxin Type A (BTX-A) and Mirror Therapy (MT) on upper extremity spasticity in stroke patients. Ethical approval was obtained from the Institutional Review Biruni University Clinical Research Ethics Committee and all participants provided written informed consent prior to enrollment in accordance with the Declaration of Helsinki (2015-KAEK-80 23 50).

Participants were selected from the neurological rehabilitation clinic of the physical medicine and rehabilitation unit at Biruni University Hospital. Eligible patients were those diagnosed with unilateral ischemic stroke and scheduled to receive BTX-A injections for upper extremity spasticity management.

Inclusion criteria were as follows:

- Age \geq 18 years
- Diagnosis of unilateral ischemic stroke confirmed by neuroimaging (MRI or CT)
- At least 3 months post-stroke to ensure chronic phase status
- Routine follow-up under the care of the same clinician who determined BTX-A treatment indication based on established clinical guidelines
- Mini-Mental State Examination (MMSE) score > 24 to ensure adequate cognitive function for participation
- Fugl-Meyer Assessment (FMA) upper extremity motor score < 55 , indicating moderate to severe motor impairment
- Modified Ashworth Scale (MAS) score between 1 and 4 in the affected upper extremity, indicating presence of spasticity

Exclusion criteria:

- Prior BTX-A or other neurotoxin injections to the affected upper extremity within the last 6 months
- Severe cognitive impairment or psychiatric disorders interfering with communication or compliance
- Concurrent participation in other experimental rehabilitation or pharmacological trials

- Visual or motor deficits severe enough to prevent effective engagement with Mirror Therapy
- History of multiple strokes or bilateral brain lesions
- Presence of neuromuscular diseases affecting the unaffected upper extremity
- Stroke etiology other than ischemic (e.g., hemorrhagic stroke, traumatic brain injury)

A total of 43 participants were initially enrolled between May 2024 and February 2025 from the neurological rehabilitation clinic of the Physical Medicine and Rehabilitation Department at Biruni University Hospital. Following baseline evaluations and BTX-A injections, participants were randomly allocated into two groups: 22 patients in the Mirror Therapy (MT) group and 21 patients in the Sham Therapy (SHA) group. Permuted block randomization was employed to ensure balanced group sizes and reduce selection bias. The randomization sequence was generated using a computer-based random number system and was implemented by an independent researcher not involved in patient assessment or treatment. Group allocation was concealed using sealed, opaque envelopes until the point of assignment.

In the MT group, 4 participants were excluded due to irregular attendance (<75% session compliance), 2 participant withdrew their informed consent, and 1 were hospitalized for unrelated medical conditions requiring inpatient treatment. In the SHA group, 4 participants failed to adhere to the intervention frequency, and 2 were excluded because they received additional pain management therapies during the follow-up period.

Consequently, 15 participants in each group (n = 30 total) completed the full 6-month intervention and follow-up assessments and were included in the final statistical analysis. The overall participant flow, including recruitment, allocation, and attrition, is illustrated in.

The study was conducted according to the approved protocol and completed as planned without early termination. The follow-up period for each participant lasted six months after BTX-A injection, and all post-treatment evaluations were completed by March 2025.

All intervention sessions were delivered by the same licensed physical therapist specialized in neurorehabilitation, ensuring procedural consistency across both groups. Adherence to the

intervention protocol was closely monitored by weekly attendance tracking and therapist supervision to maintain treatment fidelity.

Participants were allocated as follows:

- **Experimental Group (Group I, n=15):** Received mirror therapy in addition to conventional rehabilitation.
- **Control Group (Group II, n=15):** Received a sham intervention alongside conventional rehabilitation. In this group, a transparent glass panel was used in place of a mirror, and patients were instructed to observe the reflection of their paretic extremity, thereby eliminating the visual illusion effect central to mirror therapy.

A single-blind study design was implemented to minimize bias. Neither the participants nor the outcome assessors were aware of group assignments. Both the mirror therapy and sham interventions were administered by a licensed physical therapist experienced in neurorehabilitation, who was not involved in data analysis or outcome evaluation.

Evaluation Criteria

Treatment efficacy was assessed at two time points: baseline (prior to BTX-A injection) and six months post-injection. The following standardized clinical instruments were employed to evaluate motor function, spasticity, and muscle strength:

Motor Function: Assessed using the Brunnstrom Recovery Stages, with separate scoring for the hand and upper extremity. This scale provides a stage-based evaluation of motor recovery following stroke, ranging from flaccidity (Stage I) to near-normal movement patterns (Stage VI).

Spasticity: Evaluated using the Modified Ashworth Scale (MAS), which quantifies resistance during passive soft-tissue stretching. The MAS scores range from 0 (no increase in muscle tone) to 4 (rigid in flexion or extension), offering a reliable measure of spasticity severity.

Overall Motor Performance: Measured with the Fugl-Meyer Assessment for Upper Extremity (FMA-UE), a validated and widely used tool that evaluates motor function, coordination, and

reflexes in the paretic arm. Scores range from 0 to 66, with lower scores indicating more severe impairment.

Muscle Strength: Quantified using a handheld dynamometer (Jamar® or equivalent) for both the paretic and non-paretic upper extremities. Grip strength (in kilograms) was recorded as the maximum value of three consecutive trials, with standardized positioning to ensure consistency.

All assessments were conducted by a trained physiotherapist ([name]) blinded to group allocation. Standardized testing protocols were followed across all time points to ensure inter-session reliability.

Intervention Protocol

Following BTX-A injection, all participants in both groups underwent a standardized conventional upper extremity rehabilitation program for a duration of 6 months, with sessions conducted three times per week. The rehabilitation protocol included stretching exercises, passive and active-assisted range of motion exercises, coordination and balance training, as well as functional task-oriented activities. All sessions were conducted in a one-on-one setting by experienced physiotherapists.

Experimental Group (Group I): Mirror Therapy Application

In the experimental group, mirror therapy (MT) was administered in addition to conventional rehabilitation. The MT protocol was implemented as follows:

- Participants were seated upright with a large mirror placed in the midsagittal plane of the body, such that the reflection of the non-paretic extremity appeared to replace the paretic extremity.
- Movements were performed with the non-paretic extremity while patients observed the mirrored image, creating the visual illusion that the paretic extremity was moving.
- Mirror therapy was applied three times per week, with each session lasting 30 minutes, for a total of 60 sessions.
- Exercises included functional movement patterns such as finger flexion and extension, thumb abduction–adduction, and thumb opposition movements, as well as wrist flexion/extension, forearm pronation/supination, elbow flexion/extension, and simple grasp-and-release activities.

- The sequence of movements was progressively adapted to the participant's functional level, starting with isolated distal motions (finger and thumb exercises) and advancing toward combined and proximal joint movements (wrist and elbow). Patients were continuously encouraged to focus on the mirrored image to reinforce the visual illusion of symmetrical movement.

Control Group (Group II): Sham Intervention

The control group received a sham intervention designed to mimic the physical setup of mirror therapy but without inducing the visual illusion:

- A transparent glass panel was used in place of a mirror, and participants were asked to observe the reflection of their paretic extremity directly through the glass.
- This setup was intended to replicate the environment of MT without stimulating the motor cortex through visual feedback.
- The frequency, duration, and total number of sessions matched those of the experimental group (3 sessions/week, 30 minutes per session, 60 sessions in total).

All participants initiated their rehabilitation and mirror/sham therapy sessions two weeks after the BTX-A injection, coinciding with the onset of the toxin's maximal clinical effect. Adherence to the intervention protocol was strictly monitored throughout the study period.

Statistical Analysis

All statistical analyses were performed using IBM SPSS Statistics for Windows, Version 22.0 (IBM Corp., Armonk, NY, USA). The normality of continuous variables was assessed using the Shapiro-Wilk test. As the data were not normally distributed, non-parametric tests were employed for all comparisons. Continuous variables were expressed as mean \pm standard deviation (SD), and categorical variables were presented as frequencies and percentages. Between-group comparisons at baseline and post-treatment were conducted using the Mann-Whitney U test for continuous variables and the Chi-square test for categorical variables. To evaluate within-group changes from pre- to post-treatment, the Wilcoxon signed-rank test was used. In addition, Spearman's rank-order correlation coefficient (ρ) was calculated to assess the relationships between changes in motor function, spasticity, and muscle strength. A two-tailed p-value < 0.05 was considered statistically significant for all analyses. No corrections for multiple comparisons were applied, as the primary outcomes were pre-specified.

A priori sample size estimation was performed using G*Power software (Version 3.1), assuming a two-tailed test with an effect size of $d = 0.62$, $\alpha = 0.05$, and power $(1-\beta) = 0.80$. A minimum total sample size of 28 participants (13 in one group and 15 in the other) was deemed sufficient to detect statistically meaningful between-group differences.

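### The combined-effects objective is broader than the design supports if read as a joint or BTX-A effect; conclusions should rest on mirror therapy versus sham added to BTX-A

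*Combined protocol and SAP*

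**What the plan says.** The opening sentence of Study Design and Participants gives the purpose as "to investigate the combined effects of Botulinum Toxin Type A (BTX-A) and Mirror Therapy (MT) on upper extremity spasticity in stroke patients". The same sentence describes the trial as randomised and sham-controlled.

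The rest of the document fixes how BTX-A enters the trial:

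- **Eligibility.** Patients had to be "scheduled to receive BTX-A injections for upper extremity spasticity management".
- **Order of events.** "Following baseline evaluations and BTX-A injections, participants were randomly allocated into two groups". The mirror arm had 22 and the sham arm 21.
- **Background care.** The Intervention Protocol says: "Following BTX-A injection, all participants in both groups underwent a standardized conventional upper extremity rehabilitation program".
- **Arms.** The experimental group "Received mirror therapy in addition to conventional rehabilitation"; the control group "Received a sham intervention alongside conventional rehabilitation", with a transparent glass panel in place of the mirror.

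Evaluation Criteria sets two assessments, one before the injection and one six months after it. Statistical Analysis compares the groups at each of these times (Mann-Whitney U for continuous variables). It adds: "To evaluate within-group changes from pre- to post-treatment, the Wilcoxon signed-rank test was used". One two-sided 0.05 threshold covers every analysis, without multiplicity correction. The sample-size paragraph is directed at differences between groups.

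**The concern.** An objective about the combined effects of two treatments invites a conclusion about the combination. The trial randomises only one of the two. The one result that looks like a combined effect is the pre-to-post change in the mirror arm, because it starts before the toxin and ends after toxin, rehabilitation and mirror therapy together. That result has no control.

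Nothing in the plan marks the within-group tests as descriptive, and nothing confines the efficacy conclusion to the between-group comparison. A significant Wilcoxon result in the mirror arm could therefore be offered as meeting the stated objective even if the sham arm improved just as much. The protection given by randomisation and the sham would then be lost for the main claim.

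**Working it through.** No figure in the plan bears on this point. The check compares what each arm receives with what each planned test can identify.

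**1. Exposure by arm (Study Design and Participants; Intervention Protocol)**

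| | BTX-A | Conventional rehabilitation | Mirror | Sham panel | Randomised |
|---|---|---|---|---|---|
| MT group | yes | yes | yes | no | 22 |
| Sham group | yes | yes | no | yes | 21 |
| Any group without BTX-A | – | – | – | – | 0 |

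Total randomised: 22 + 21 = 43, all injected before allocation. BTX-A is a constant of the trial, not a factor in it.

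**2. What the between-group comparison identifies**

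As a bookkeeping device, write the expected change in each arm as a sum:

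- MT arm: T + R + N + G + M
- Sham arm: T + R + N + G + S

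Here T is any toxin effect still present at six months, R rehabilitation, N natural recovery, G regression to the mean, M the effect of mirror therapy in BTX-A-treated patients, and S the effect of the sham. The difference is

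(T + R + N + G + M) − (T + R + N + G + S) = M − S.

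This is mirror versus sham, given BTX-A and rehabilitation. Any interaction between mirror therapy and the toxin is contained in M and cannot be separated from it.

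**3. What other readings of the objective would need**

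- Effect of BTX-A: a comparison with and without the toxin. There are 0 participants without it.
- Joint effect of both against neither: two cells (BTX-A with mirror; neither). One exists.
- Interaction or synergy: four cells (with or without BTX-A, crossed with mirror or sham). Two exist.

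**4. What the within-group Wilcoxon test identifies**

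In the MT arm it tests whether T + R + N + G + M is zero. Suppose mirror therapy does nothing beyond sham, so that M = S. The sum can still differ from zero:

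- baseline precedes the injection, so T is included;
- rehabilitation ran three times a week for six months, so R is included;
- entry is allowed from 3 months after stroke, so N need not be zero;
- patients were selected on impairment (FMA upper-extremity score below 55, MAS of 1 to 4, and a clinical indication for BTX-A), so G need not be zero.

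Rejection is therefore compatible with no benefit of mirror therapy over sham. The documents do not say how much toxin effect remains at six months. The argument does not depend on it, because R, N and G remain even if T is zero.

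**5. Where change is tested**

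The Mann-Whitney comparisons are described at baseline and post-treatment; none is described on change scores. Spearman coefficients relate changes in different outcomes to one another. The only tests of whether an outcome changed are thus the uncontrolled Wilcoxon tests.

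**The case against.** The strongest reply is that *combined* need not mean a factorial or joint effect. In an add-on trial it can mean mirror therapy used together with BTX-A, and much of the text supports this: the sham replaces the mirror and not the toxin, the arms are named for mirror and sham, patients were due for BTX-A anyway, and the sample size is aimed at between-group differences. On that reading the Mann-Whitney comparison answers the objective. This stands. A reader might infer that the objective cannot be answered at all, but the documents do not support that.

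A reader might also infer that the plan claims synergy or treats pre-to-post change as proof of efficacy. It does neither. The document contains no results and mentions neither synergy nor interaction. The Wilcoxon tests are planned in both arms beside a between-group test, so a similar change under sham would be visible.

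What remains is that no section states the narrower question or limits the efficacy conclusion to the randomised comparison, while the uncontrolled tests carry the same significance threshold.

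**Conclusion.** The point holds in a limited form. The trial supports one randomised contrast: mirror therapy versus sham in patients given BTX-A and concurrent conventional rehabilitation. It cannot identify a BTX-A effect, a joint effect against neither treatment, or an interaction, because 0 of 43 participants were without BTX-A. No choice of test or sample size alters that. The within-group tests cannot support a conclusion that the combination works.

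This is a gap between the wording of the objective and the inference available, not a failed design. Restating the objective changes no arm, no between-group test and no number, but it does change what may be concluded.

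The verdict assumes that allocation and background care were as described. It takes the between-group comparison as planned. That only 30 of the 43 randomised were analysed (15 per group), and whether the stated sample size follows from its inputs, are separate matters that neither add to this point nor weaken it.

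**What to change.** 1. Restate the objective: *to estimate the effect of adding mirror therapy, versus sham, on spasticity of the upper extremity in people with stroke who have been treated with BTX-A and are receiving concurrent conventional rehabilitation.* Keep spasticity in the sentence. Statistical Analysis refers to pre-specified primary outcomes without naming them, and the objective is the only pointer to one. Call rehabilitation concurrent, because it started together with the mirror or sham sessions two weeks after injection.
2. State in Statistical Analysis that the efficacy conclusion rests only on the between-group comparison.
3. Label the within-group Wilcoxon results descriptive, and report both arms side by side.
4. Make no claim about a BTX-A effect, a joint effect or synergy.

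This takes a few sentences and no new data, and it remains possible although follow-up is complete. The price is a narrower claim: the trial can speak about mirror therapy on a BTX-A background, not about the combination as such.

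### Time since stroke has a 3-month floor but no upper limit, stratification or adjustment, which leaves room for chance imbalance and some lost precision at 15 per arm

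*Combined protocol and SAP*

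**What the plan says.** The inclusion criteria under Study Design and Participants of the combined protocol and SAP contain one rule on time since stroke: "At least 3 months post-stroke to ensure chronic phase status". Neither the inclusion nor the exclusion list sets an upper limit, and the variable is not mentioned again.

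On allocation, the same section says: "Permuted block randomization was employed to ensure balanced group sizes and reduce selection bias". No stratification factor is named. The sequence was computer-generated and concealed, and it gave "22 patients in the Mirror Therapy (MT) group and 21 patients in the Sham Therapy (SHA) group". After exclusions, "15 participants in each group (n = 30 total) completed the full 6-month intervention and follow-up assessments and were included in the final statistical analysis".

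On follow-up: "The follow-up period for each participant lasted six months after BTX-A injection". Under Evaluation Criteria, outcomes are taken only at baseline and at six months.

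The Statistical Analysis section says: "Between-group comparisons at baseline and post-treatment were conducted using the Mann-Whitney U test for continuous variables". Categorical variables are compared by Chi-square and within-arm change by the Wilcoxon signed-rank test. No covariate model is described. Baseline comparisons are planned, but their variables are not listed, and testing for baseline differences adjusts for nothing.

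**The concern.** The plan treats time since stroke as important enough to restrict entry on, then leaves it out of both the allocation and the analysis. The rule admits a patient at month 3, followed to month 9, alongside a patient many years after stroke. If the more recent patients improve more over six months whatever the therapy, two things follow. An arm that happens to hold more of them will show a larger gain. And the spread between recent and late patients adds noise to the arm comparison even when the arms are balanced.

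With 15 analysed per arm, neither effect can be ignored. The single baseline and single follow-up visit offer no way to see whether a patient was stable at entry. The within-arm Wilcoxon tests cannot separate natural recovery from treatment in either arm, so the between-arm comparison has to carry the inference.

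**Working it through.** The plan gives no figure for the effect of time since stroke, so there is none to reproduce. The planned effect size d = 0.62 serves below only as a yardstick. (The stated total of 28 does not follow from d = 0.62, which needs 84 by a two-sided two-sample t test at 80% power. That is a separate matter, but it explains the low starting power in step 5.)

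**Inputs from the documents:** 22 and 21 randomised; 15 and 15 analysed; two-sided alpha 0.05; d = 0.62.

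**Assumed, because the documents are silent:** the share q of patients with a recent stroke (the first months after the floor), their extra gain, and the correlation of time since stroke with outcome.

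1. *Losses after randomisation.* Mirror therapy: 4 + 2 + 1 = 7 of 22 (31.8%). Sham: 4 + 2 = 6 of 21 (28.6%). Together 13 of 43 (30.2%), of whom 4 + 4 = 8 were removed for attendance or adherence.

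2. *Chance imbalance.* Taking the number of recent-stroke patients in each arm as Binomial(15, q), the exact probabilities are:

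| q (assumed) | Arms differ by 3 or more | Arms differ by 4 or more |
|---|---|---|
| 0.2 | 0.25 | 0.11 |
| 0.3 | 0.32 | 0.16 |
| 0.5 | 0.36 | 0.20 |

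For any continuous baseline variable, the standard error of the standardised arm difference is sqrt(2/15) = 0.365, so a difference above 0.5 SD occurs with probability 17%.

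3. *Size of the shift.* The SD of the chance shift in the arm difference is gain × sqrt(2q(1−q)/15). At q = 0.3 the root is sqrt(0.42/15) = 0.167. Assumed extra gains of 3, 6 and 10 FMA-UE points give 0.50, 1.00 and 1.67 points. In SD units, an imbalance of 4 in 15 with an assumed extra gain of 0.5 to 1.0 SD shifts the difference by 4/15 × 0.5 = 0.13 to 4/15 × 1.0 = 0.27 SD, or 22% to 43% of 0.62.

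4. *Type I error.* Mann-Whitney test, 15 v 15, no treatment effect, q = 0.3, 20,000 simulated trials per case:

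| Extra gain (assumed) | Overall | Given imbalance of 4 or more |
|---|---|---|
| 0.5 SD | 4.6% | 6.0% |
| 1.0 SD | 4.8% | 9.2% |

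5. *Precision.* Adjusting for a covariate with correlation ρ to the outcome raises the effective effect size to d/sqrt(1−ρ²). Power is from the two-sample t test at 15 v 15, without deducting the covariate's degree of freedom:

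| ρ (assumed) | Effective d | Power |
|---|---|---|
| 0 (unadjusted) | 0.62 | 37% |
| 0.2 | 0.63 | 39% |
| 0.3 | 0.65 | 40% |
| 0.5 | 0.72 | 47% |

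**The case against.** The strongest reply is that randomisation already deals with this. Allocation was computer-generated and concealed, and a concurrent sham arm on the same schedule undergoes the same natural recovery. What remains is sampling error, which the Mann-Whitney p-value covers. This stands: step 4 shows overall type I error of 4.6% to 4.8%. A reader might infer that uneven recovery biases the arm comparison by design; the documents do not support that. The reply is weaker for the analysed set than for the randomised set, because 13 patients were removed after allocation. If removal depended on time since stroke differently in the two arms, balance on average would be lost. The documents neither show nor exclude this.

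Second, the sizes rest on assumptions and may be small. With an assumed FMA-UE change SD of 8 to 12, the standard error of the arm difference is 0.365 × 8 = 2.9 to 0.365 × 12 = 4.4 points. The middle case in step 3 (SD 1.00) is already part of that. It accounts for 36 × 0.3 × 0.7 = 7.56 out of 64 to 144, or 12% to 5%, of the variance, so adjustment would narrow the standard error by about 6% to 3%. This also stands, and nothing has been computed for the Modified Ashworth Scale.

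Third, a reader might infer that 3 months is too early to be called chronic. Nothing in the documents settles that; it would need an outside source. Nor do they draw a conclusion about chronic stroke: the word appears once, in the entry criterion, and the objective speaks of stroke patients.

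Fourth, eligibility requires only that 3 months have passed. A recorded stroke date is implied but not stated.

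**Conclusion.** The point holds as one of precision and robustness. Time since stroke is not capped, balanced by design or modelled. Randomisation balances it on average and keeps overall type I error near 5%. With 15 analysed per arm, a chance imbalance of 3 or more recent-stroke patients is plausible (about 25% to 36% of trials if 20% to 50% are recent). It would be wrong to call it likely, since 64% to 75% of trials would show less.

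Where an imbalance of 4 or more does arise, it could move the arm difference by 0.13 to 0.27 SD under the assumed extra gains. The expected benefit of adjustment is modest: power at d = 0.62 goes from 37% to about 39% to 47% for assumed correlations of 0.2 to 0.5. All these sizes depend on shares, gains and correlations that the documents do not give. The absence of an upper limit, stratification and adjustment is read directly from the text.

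**What to change.** - Add a between-arm analysis adjusted for time since stroke at injection together with the baseline score of the outcome. Rank ANCOVA does both, with time since stroke continuous on the log scale so that no cut-point has to be chosen. A van Elteren test stratified by time since stroke is an alternative, but by itself it does not bring in the baseline score.
- Because data collection is complete, label this a sensitivity analysis and show it beside the planned Mann-Whitney test. A cut-point chosen now cannot be presented as pre-specified.
- Report the distribution of time since stroke by arm, for the 43 randomised as well as the 30 analysed, so that the reader can see whether the exclusions disturbed the balance.
- Describe the population as at least 3 months post-stroke, in place of the claim that the floor secures a chronic phase.

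Cost: no new patients or visits, and one or two degrees of freedom. The analysis is post hoc and its expected gain is modest. It depends on the stroke date having been recorded; if it was not, say so as a limitation.

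### The only analysis leaves out 11 of the 43 randomised participants for events that happened after randomisation

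*Combined protocol and SAP*

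**What the plan says.** The Study Design and Participants section describes baseline assessment and BTX-A injection, followed by random allocation: "22 patients in the Mirror Therapy (MT) group and 21 patients in the Sham Therapy (SHA) group". It then accounts for the losses arm by arm.

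- Mirror therapy (MT): "In the MT group, 4 participants were excluded due to irregular attendance (<75% session compliance"; two more withdrew consent, and "1 were hospitalized for unrelated medical conditions requiring inpatient treatment".
- Sham: "In the SHA group, 4 participants failed to adhere to the intervention frequency, and 2 were excluded because they received additional pain management therapies".

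The remaining 15 per arm "completed the full 6-month intervention and follow-up assessments and were included in the final statistical analysis". The eligibility lists in the same section contain no rule for removing a participant later because of attendance or pain treatment.

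The Statistical Analysis section gives the test ("Between-group comparisons at baseline and post-treatment were conducted using the Mann-Whitney U test") but not the set of participants it applies to. It names no as-randomised population, no way of handling missing outcomes and no sensitivity analysis.

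**The concern.** Randomisation makes the two arms comparable at the moment of allocation. Removing people for what they did, or what happened to them, afterwards gives up that guarantee. Attendance, need for extra pain treatment and admission to hospital can each be related to how a participant is recovering. The 15 v 15 contrast therefore compares those who stayed on protocol in each arm, not the groups that were formed by chance.

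This holds even if one adherence rule was applied to both arms, because the people who fall below a threshold on mirror therapy need not resemble those who fall below it on sham. With no second analysis, a reader cannot tell whether a six-month difference depends on who was left out.

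**Working it through.** **Inputs.** All counts come from the participant-flow text in Study Design and Participants. The planned effect size, d = 0.62, comes from Statistical Analysis.

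**Step 1: reproduce the analysed numbers.**

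| | MT | Sham | Total |
|---|---|---|---|
| Randomised | 22 | 21 | 43 |
| Poor adherence | 4 | 4 | 8 |
| Added pain therapy | 0 | 2 | 2 |
| Hospitalised | 1 | 0 | 1 |
| Consent withdrawn | 2 | 0 | 2 |
| Analysed | 22 − 4 − 1 − 2 = 15 | 21 − 4 − 2 = 15 | 30 |

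The plan's 15 + 15 = 30 reproduces exactly.

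**Step 2: size of the exclusion.** Left out in all: MT 7/22 = 31.8%, sham 6/21 = 28.6%, total 13/43 = 30.2%. Left out for reasons other than consent: 5 MT + 6 sham = 11, and 11/43 = 25.6%.

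**Step 3: the largest set that could be restored.** Taking the two consent withdrawals to cover use of data, MT is at most 15 + 4 + 1 = 20 and sham at most 15 + 4 + 2 = 21. That is 41/43 = 95.3% of those randomised, against 30/43 = 69.8% now. If the hospitalised participant has no six-month outcome, it is 19 + 21 = 40, or 93.0%.

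**Step 4: possible shift in the contrast.** Suppose the excluded differ in mean outcome from the analysed in the same arm by x SD. The completer mean then differs from the mean of the restored arm by (excluded ÷ restored) × x:

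- MT only: 5/20 × x = 0.250x
- Sham only: 6/21 × x = 0.286x
- Same x and same direction in both arms: (0.286 − 0.250)x = 0.036x

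| Assumed x (SD) | One arm only (SD) | Share of d = 0.62 | Equal in both arms (SD) |
|---|---|---|---|
| 0.25 | 0.063 to 0.071 | 10 to 12% | 0.009 |
| 0.5 | 0.125 to 0.143 | 20 to 23% | 0.018 |
| 1 | 0.250 to 0.286 | 40 to 46% | 0.036 |

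The values of x are assumptions; the documents give none. The planned test uses ranks, so the mean shifts are a guide to scale only.

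**Step 5: precision.** The standard error of a standardised difference is √(1/n₁ + 1/n₂). For 15 v 15 it is √(1/15 + 1/15) = 0.365; for 20 v 21 it is √(1/20 + 1/21) = 0.312. The reduction is 1 − 0.312/0.365 = 14%. This is a ceiling: it needs all 11 outcomes to exist and the spread to stay the same.

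**The case against.** The strongest objection is that the missing data may not exist. The text describes the 15 per arm as those who finished both the treatment and the follow-up assessments, which suggests that at least some of the 11 were never assessed at six months. If so, 20 v 21 and the 14% gain are out of reach, and rerunning the same test on whoever has an outcome is still an available-case analysis. This stands. It means the remedy must include a count of missing outcomes and some way of handling them, and it may end with a relabelled result rather than a new one. It does not justify leaving the analysis set undefined.

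Second, the losses look balanced: 4 v 4 for adherence and 7/22 v 6/21 overall. Under equal selection the shift is negligible. This also stands, in part. Equal counts do not establish equal prognosis, and the other reasons differ by arm: pain therapy removed sham participants only, and hospitalisation an MT participant only. But the one-arm figures rest on assumed differences and are not evidence that bias of that size occurred.

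Third, the participant-flow figure is not reproduced in the text available and may say more about outcome availability or reasons for exclusion. The point therefore does not depend on silence about those details. It rests on what the text states was analysed and on the absence of any other set in Statistical Analysis.

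Fourth, a reader might infer that sham was held to a different adherence rule, because the 75% figure appears only for MT. The documents do not support that. The Intervention Protocol matches frequency, duration and number of sessions between arms, and adherence monitoring is described without distinguishing them. Different wording does not show a different rule.

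**Conclusion.** The concern holds. The reported comparison is a completer, or per-protocol, analysis of 30 of 43 randomised participants; 11 (25.6%) were left out for post-randomisation reasons other than consent, and nothing is planned beside it. Bias is possible but not shown. It is 0.04 SD or less if the excluded differ equally in both arms by up to 1 SD, and about 0.13 to 0.14 SD (20 to 23% of the planned d) if they differ by an assumed 0.5 SD in one arm only.

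Stronger inferences are tempting and should be resisted:

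- A reader might conclude that the exclusions favoured mirror therapy. No outcome data on the excluded are given, so no direction can be claimed.
- A reader might take the six-month intervention wording as contradicting the 60 sessions at three per week (60/3 = 20 weeks). The Intervention Protocol gives six months to conventional rehabilitation, which can explain the phrase.
- The group list shows "Experimental Group (Group I, n=15" and "Control Group (Group II, n=15" as allocated numbers. The true 22 and 21 stand earlier in the same section, so this is an editorial slip that conceals nothing.

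Whether the enrolment and completion dates allow six months of follow-up for late enrolees is a separate question, and this point does not rest on it.

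**What to change.** 1. Make the main comparison as randomised, with the same Mann-Whitney test. Keep every participant who has a six-month outcome and has not withdrawn consent to data use, whatever their attendance, added pain therapy or hospitalisation. That gives at most 20 MT and 21 sham.
2. Report missing six-month outcomes per arm, with reasons. Where any of the 11 have none, say so and add a simple sensitivity analysis, for example baseline carried forward (baseline was assessed before allocation) or best and worst ranks assigned to the missing.
3. Label the 15 v 15 result as the per-protocol sensitivity analysis, with one adherence threshold for both arms: 75% of scheduled sessions. Counted on the 60 mirror or sham sessions, that is 0.75 × 60 = 45. If a recount changes who qualifies, report the new numbers.
4. If no further outcomes exist, present the conclusion as per-protocol only.

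The cost is low: a check of which outcomes are on file, a recount from the weekly attendance records, a rerun of the existing tests and some text changes. There are two downsides. Including low attenders may dilute the estimate towards the effect of being assigned mirror therapy, though the per-protocol result still shows the adherent participants. And some outcomes may be unavailable, in which case the missing-data analysis narrows the uncertainty but does not remove it.
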